5.4.2 Ibrutinib

The ibrutinib dose should be held for any unmanageable toxicity that is consistent with the rules outlined in Section 5.4.1. Dose should be modified according to the dose modification guidelines in Table 3. See Table 4 for dose reduction levels for ibrutinib.

Please see Sections 10.2.2.1 and 10.2.2.2 for reporting of major hemorrhage and intracranial hemorrhage.

Table 4. Dose Reduction Levels for Ibrutinib.

Dose Level	Ibrutinib Dose
Level -1	420 mg per day

Proprietary Information of MD Anderson

Level -2	280 mg per day
Level -3	140 mg per day
Level -4	Discontinue ibrutinib

The dose of ibrutinib may be reduced successively by one level from starting dose, Table 4. Once a patient's dose has been reduced, no dose re-escalation is permitted. Patients who cannot tolerate the lowest applicable dose level are to be discontinued from the Treatment Phase. Patients with mild hepatic impairment will be starting at 140mg per day as outlined in Table 1. If these subjects have toxicity that result in dose modification of ibrutinib as outlined above, they will be discontinued from the Treatment Phase as they are starting at the lowest applicable dose level and cannot tolerate therapy.

Please see Section 6.1.2.1 for guidelines for management of ibrutinib in subjects who require treatment with a strong CYP3A4/5 inhibitor.

5.4.3 Rituximab

The rituximab dose should be held for any unmanageable toxicity that is consistent with the rules outlined in Table 3. A missed dose of rituximab on the weekly schedule for any reason will not be made up (the visit window for this visit and Day 1 of Cycles 2 -12 is ± 2 days).

5.4.4 Lenalidomide

The lenalidomide dose should be held for any unmanageable toxicity that is consistent with the rules outlined in Table 3.

The dose of lenalidomide may be reduced successively by one level from starting dose, Table 5. Once a patient's dose has been reduced, no dose re-escalation is permitted. Patients who cannot tolerate the lowest applicable dose level are to be discontinued from the Treatment Phase. Dose modification should also meet the specifications outlined for those subjects with renal insufficiency as outlined in Table 2. If patients with renal impairment are currently receiving 10mg every 24 hours and need a dose modification, they will then be dose reduced to 15mg every 48 hours. If they need further dose reduction due to toxicity, they will be discontinued due to being unable to tolerate the lowest applicable dose. Similarly, patients starting at 15mg every 48 hours who need further dose reduction will be discontinued due to being unable to tolerate the lowest applicable dose.

Table 5. Dose Reduction Levels for Lenalidomide

Dose Level	Lenalidomide 15 mg starting dose	Lenalidomide 20 mg starting dose
Level -1	10mg daily on Days 1-21, every 28 days	15mg daily on Days 1-21, every 28 days

Proprietary Information of MD Anderson

Level -2	5mg daily on Days 1-21, every 28 days	10mg daily on Days 1-21, every 28 days
Level -3	Discontinue lenalidomide	5mg daily on Days 1-21, every 28 days

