5.3 Treatment Schedule

Patients will receive 12 cycles of lenalidomide, 15mg daily on days 1-21 of cycle 1, and 20mg daily on days 1-21 (± 2 days) of cycles 2 through 12. Cycles will be 28 days in length. Patients will receive rituximab, 375mg/m² on days 1, 8 (± 2 days), 15 (± 2 days), and 22 (± 2 days) of cycle 1, and day 1 (± 2 days) of cycles 2 through 12. Patients will receive ibrutinib 560mg daily, starting on day 1 of cycle 1 and continued through 12 cycles. Therapy is continued for 12 cycles or until disease progression, unacceptable toxicity, or voluntary withdrawal.

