5.4.1 Toxicities Necessitating Dose Modification or Delay

Toxicities necessitating dose modification or delay will be defined as any non-hematologic or hematologic toxicity listed below. Study treatment should be discontinued in the event of a toxicity lasting more than 28 days despite appropriate medical management, unless reviewed and approved by the Principal Investigator. The action in Table 3 should be taken for the following toxicities:

Proprietary Information of MD Anderson

Non-hematologic toxicity will be defined as any of the following:

- Any unmanageable Grade 3 or 4 non-hematologic toxicity with failure to improve (< Grade 2) or recover to baseline within 14 days of withholding drug
- Grade 3 or 4 non-blistering rash that does not resolve to < Grade 2 within 14 days
- Any desquamating (blistering) rash
- Any grade Stevens-Johnson syndrome or toxic epidermal necrolysis
- Grade 3 or 4 thrombosis/embolism
- Grade 3 or 4 peripheral neuropathy which began or worsened while on study

Hematologic toxicity will be defined as any of the following:

- Grade 3 neutropenia with infection or fever (single temperature of > 38.3 °C, or with a sustained temperature of ≥ 38 °C lasting > 1 hour).
- Grade 4 neutropenia (ANC<500/µL) lasting > 7 days.
- Grade 4 thrombocytopenia (<25,000/µL)

The following action should be taken for any unmanageable toxicity that is consistent with the rules outlined above:

Table 3. Dose modification for toxicity

Toxicity Grade	Action to be Taken
Grade 3 neutropenia associated with fever (single temperature of > 38.3 °C, or with a sustained temperature of ≥ 38 °C lasting > 1 hour)	
• Hold lenalidomide and ibrutinib.• Follow CBC weekly.• If neutropenia has resolved to < Grade 2 prior to Day 21 of the current cycle, restart lenalidomide at next lower dose level, (see Table 5) and continue through the scheduled Day 21 of the current cycle. Otherwise, omit for remainder of cycle and reduce the dose of lenalidomide by 1 dose level at the start of the next cycle.
OR	
• Withhold ibrutinib until recovery to < Grade 2 or baseline; may restart at original dose level for the first occurrence. For subsequent occurrence, please refer to Table 4 for next lower dose level.• Withhold rituximab until recovery to < Grade 2 or baseline.• Omitted doses are not made up.• G-CSF may be used

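### Lenalidomide reductions have no defined reference dose: a reduction deferred from Cycle 1 to Cycle 2 gives 10 mg or an unreduced 15 mg, and the step to 20 mg is not reconciled with the ban on re-escalation

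*Combined protocol and SAP*

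**What the plan says.** - **Schedule.** Section 5.3: "Patients will receive 12 cycles of lenalidomide, 15mg daily on days 1-21 of cycle 1, and 20mg daily on days 1-21" for Cycles 2 to 12. Section 5.3.1 and Table 2 repeat this for creatinine clearance above 60 mL/min. None of the three makes the Cycle 2 step depend on how Cycle 1 was tolerated.
- **Reduction rule.** Section 5.4.4: "The dose of lenalidomide may be reduced successively by one level from starting dose, Table 5". It adds: "Once a patient's dose has been reduced, no dose re-escalation is permitted".
- **Ladders.** Table 5 has two columns, headed "Lenalidomide 15 mg starting dose" and "Lenalidomide 20 mg starting dose". Level -1 is 10 mg in the first and 15 mg in the second.
- **When the reduction takes effect.** For febrile Grade 3 neutropenia, Grade 4 thrombocytopenia, a second Grade 3 or higher non-blistering rash and Grade 3 neuropathy, Table 3 (Section 5.4.1) has two branches. If the toxicity resolves far enough before Day 21, lenalidomide restarts in the same cycle one level lower. If not, the instruction is to "omit for remainder of cycle and reduce the dose of lenalidomide by 1 dose level at the start of the next cycle".

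**The concern.** A rule that reduces from the starting dose works when the planned dose is constant. Section 5.4.2 uses the same sentence for ibrutinib without difficulty, because Table 4 is a single ladder. For lenalidomide the planned dose rises at Cycle 2, and nothing says whether the starting dose means the dose on Cycle 1 Day 1 or the dose scheduled for the cycle being started. Under the first meaning nobody belongs in the 20 mg column, since no Cycle 1 entry in Table 2 is 20 mg. Under the second, a subject changes column at the moment a deferred reduction is applied.

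What is at stake:

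- **Safety.** Two clinicians who follow the text after the same serious toxicity could give different Cycle 2 doses, one of them not reduced.
- **Compliance.** Section 5.5 calls any dose above the specified one an overdose. In Cycle 2, 15 mg would be compliant under one column and an overdose under the other.
- **Reporting.** Section 3.2.2 makes adverse events that require dose reduction a secondary safety endpoint. A move from 15 mg to 15 mg could be counted as a one-level reduction or as none.
- **Monitoring.** The affected doses fall in Cycles 1 and 2, the window of the toxicity stopping rule in Section 9.6.

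**Working it through.** The plan gives no figure to reproduce. The check is to read the Cycle 2 dose from each passage for one subject, and the only arithmetic is comparison with the Cycle 1 dose.

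**Subject.** Creatinine clearance above 60 mL/min throughout, 15 mg daily in Cycle 1, and a Cycle 1 toxicity for which Table 3 requires a one-level lenalidomide reduction.

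**Inputs.** Cycle 1 dose 15 mg and scheduled Cycle 2 dose 20 mg (Sections 5.3 and 5.3.1, Table 2); Level -1 of 10 mg in the 15 mg column and 15 mg in the 20 mg column (Table 5); timing of the reduction (Table 3); no re-escalation (Section 5.4.4). Percentage change = (Cycle 2 dose - 15) / 15. Cycle total = 21 days x daily dose.

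**Branch 1: not resolved before Day 21, reduction applied at the start of Cycle 2**

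| Reading of starting dose | Cycle 2 dose | Change from Cycle 1 dose | Total over 21 days |
|---|---|---|---|
| 15 mg column | 10 mg | (10 - 15)/15 = -33% | 21 x 10 = 210 mg |
| 20 mg column | 15 mg | (15 - 15)/15 = 0% | 21 x 15 = 315 mg |

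A full Cycle 1 is also 21 x 15 = 315 mg. The second reading therefore satisfies the instruction to go down one level and leaves the daily dose where it was when the toxicity occurred. The ban on re-escalation does not clearly choose between the rows, because no reduced dose has yet been given.

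**Branch 2: resolved before Day 21, restarted one level lower within Cycle 1**

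1. The subject has received only 15 mg, so the 15 mg column applies and the restart dose is 10 mg.
2. The ban on re-escalation in Section 5.4.4 then holds Cycle 2 at no more than 10 mg.
3. Sections 5.3 and 5.3.1 and Table 2 schedule 20 mg for the same day with no exception, 20 - 10 = 10 mg above the reduced dose.
4. No passage says whether the planned step counts as re-escalation or is overridden by a reduction. The ibrutinib paragraph of Section 5.3.1 points to Section 5.4 for toxicity; the lenalidomide paragraph does not.

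**Hold without reduction.** For a first Grade 3 or higher non-blistering rash, Table 3 holds lenalidomide and then restarts it at the original level, or omits it for the rest of the cycle. No passage says whether the step to 20 mg then goes ahead. This is a gap in the text, not a contradiction. Section 1 reports Grade 3 rash in 8 of 22 subjects on this combination, without its timing.

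**The case against.** The strongest reply is that Section 5.3 is the default schedule and Section 5.4 modifies it, as in any protocol. On that view the two Table 5 columns simply match the two scheduled doses, and a sensible clinician would not raise the dose after a reduction.

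Much of this stands:

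- **20 mg as a third dose.** A reader might infer that the plan offers three Cycle 2 doses after a dose-reducing toxicity, one of them an increase on Cycle 1. The documents do not support that. Table 3 requires a reduction and Section 5.4.4 bars re-escalation, so 20 mg arises only if Section 5.3 is read alone. What remains is an unconditional step-up that conflicts with those two rules and is nowhere stated to yield to them.
- **Branch 2.** The 15 mg column and the ban on re-escalation largely settle it at 10 mg. The unresolved choice of dose is in Branch 1.
- **Later cycles.** A subject already taking 20 mg fits the 20 mg column naturally. Going from 20 mg to 10 mg would skip a level, against the one-level wording.
- **Ladder endings.** One column ends in discontinuation and the other at 5 mg, but 5 mg is the lowest dose in both. Section 5.4.4 takes anyone who cannot tolerate the lowest level off treatment.

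The reply does not reach Branch 1. If the columns match the scheduled doses, a reduction applied at the start of Cycle 2 meets a scheduled dose of 20 mg and returns 15 mg. If they match the dose taken when the toxicity occurred, it returns 10 mg. Both are reasonable readings, and no sentence decides between them.

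**Conclusion.** The point holds, within limits. For a Cycle 1 toxicity whose reduction is deferred to Cycle 2, the text supports either 10 mg or 15 mg, and the second is no reduction. The gap is 5 mg a day, or 315 - 210 = 105 mg over a 21-day course. For a reduction made within Cycle 1, the scheduled step to 20 mg conflicts with Table 3 and Section 5.4.4, and its override is left unstated. Because the conflict can leave a serious toxicity without an actual reduction, it bears on safety and should be corrected.

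The conclusion assumes creatinine clearance stays above 60 mL/min and that Table 3 calls for a lenalidomide reduction. Three further inferences are not supported:

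- **How many subjects are affected.** The 25% Grade 3 and 10% Grade 4 neutropenia in Section 1 might be used to estimate this. They are not the Section 5.4.1 triggers, which need fever or infection with Grade 3, or more than 7 days at Grade 4. The same paragraph puts febrile neutropenia below 1%.
- **Variation between sites.** This is a single-center study (Section 3.1), so any inconsistency would be between clinicians.
- **A shift in the stopping rule.** Section 9.6 counts treatment-related death and frequent discontinuation. Running down a Table 5 ladder takes several reductions, so any effect on the boundary is indirect and has not been quantified.

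**What to change.** Reconcile Sections 5.3 and 5.3.1, Table 2, Table 3 and Section 5.4.4 with Table 5:

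1. State one reference dose for Table 5 reductions, for example by defining it as either the dose at the time of the toxicity or the dose scheduled for the cycle being started, and reword the column headings to match.
2. State in Section 5.3 and Table 2 whether the Cycle 2 step-up applies after a Cycle 1 hold, and whether it applies after a Cycle 1 reduction, so that the schedule agrees with the ban on re-escalation.
3. Add a pointer to Section 5.4 in the lenalidomide paragraph of Section 5.3.1.

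Which dose applies in each case is for the sponsor's clinical team to decide. The cost is an edit to protocol wording and tables, with no extra subjects, visits or procedures.

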5.5 Overdose Instructions

Any dose of study drug in excess of that specified in this protocol is considered to be an overdose. Signs and symptoms of an overdose that meet any SAE criterion must be reported as an SAE in the appropriate time frame and documented as clinical sequelae of an overdose. In the event of an overdose, subjects should be closely monitored and given appropriate supportive treatment.

5.6 Criteria for Permanent Discontinuation of Study Drug

Investigators are encouraged to keep a subject who is experiencing a clinical benefit on study unless significant toxicity puts the subject at risk or routine noncompliance puts the study outcomes at risk. If a subject meets any of the following criteria, then withdrawal from the study treatment is mandatory:

- Subject has confirmed progressive disease (PD)
- Subject has an intercurrent illness or AE that prevents further treatment administration beyond 28 days
- Subject decides to withdraw from study
- Subject becomes pregnant
- Subject is routinely noncompliant with study procedures and/or scheduled evaluations
- Subject requires a prohibited concomitant medication
- Investigator considers withdrawal to be in the best interest of the subject.

A safety follow up visit is required for all subjects except those who have withdrawn full consent.

6. CONCOMITANT MEDICATIONS/PROCEDURES

6.1 Concomitant Medications

6.1.1 Permitted Concomitant Medications

Supportive medications (such as for emesis, diarrhea, constipation, etc.) should be delivered in accordance with standard practice. Tumor lysis prophylaxis should be administered during cycle 1 as clinically indicated in accordance with standard practice. Of note, aprepitant is a moderate CYP3A4/5 inhibitor and should be used with caution as outlined below in Section 6.1.2.1. Use of neutrophil growth factors (granulocyte colony-stimulating factor [G-CSF] such as filgrastim or pegfilgrastim) is permitted for management of neutropenia in accordance with the American Society of Clinical Oncology (ASCO) guidelines. Preemptive or prophylactic G-CSF during cycle 1 is not required. Transfusions may be given in accordance with institutional policy.

Proprietary Information of MD Anderson

Short courses of corticosteroids (<14 days) for treatment of non-lymphoma related medical reasons (e.g. rash, arthritis, asthma) or for tumor flare at doses that do not exceed 10mg per day of prednisone or equivalent are permitted, See Section 6.1.3. However, if clinically indicated, higher doses of corticosteroids (>10mg per day) are permissible.

6.1.2 Concomitant Medications to be used with Caution

6.1.2.1 Concomitant use of CYP3A4/5 Inhibitors/Inducers

Ibrutinib is metabolized primarily by CYP3A4/5. Due to the potential increase in ibrutinib exposure, concomitant use of strong CYP3A4/5 inhibitors (e.g., ketoconazole, indinavir, nelfinavir, ritonavir, saquinavir, clarithromycin, telithromycin, itraconazole, and nefazadone) should be avoided while the subject is receiving treatment.

If use of a strong CYP3A4/5 inhibitor is necessary, selection of an alternate concomitant medication with less potent enzyme inhibition potential is strongly recommended. If concomitant use of ibrutinib with a strong CYP3A4/5 inhibitor is unavoidable, ibrutinib should be discontinued. After completing treatment with the strong CYP3A4/5 inhibitor, wait at least 7 days before resuming ibrutinib.

Subjects should avoid grapefruit and Seville oranges during ibrutinib treatment, as these contain moderate inhibitors of CYP3A4/5. In addition, moderate CYP3A4/5 inhibitors commonly used include aprepitant, diltiazem, verapamil, erythromycin, and fluconazole. These moderate CYP3A4/5 inhibitors should be avoided, but if necessary are permissible and should be used with caution.

Co-administration of ibrutinib with strong CYP3A4/5 inducers (e.g., carbamazepine and rifampin) may decrease ibrutinib plasma concentrations and should be avoided.

A comprehensive list of inhibitors, inducers, and substrates may be found at www.fda.gov/Drugs/DevelopmentApprovalProcess/DevelopmentResources/DrugInteractionsLabeling/ucm093664.htm#cypEnzymes

or

<http://medicine.iupui.edu/clinpharm/ddis/table.aspx>. These websites are revised continually and should be checked for updates.

6.1.2.2 Thromboembolism Prophylaxis

Aspirin and Heparin

It is recommended that patients who are at high risk for a thromboembolic event (history of a thromboembolic event, taking concomitant medications associated with an increased risk for a thromboembolic event, a known hypercoagulable state regardless of thromboembolic history) receive prophylactic aspirin (81mg) daily unless contraindicated. If aspirin is contraindicated, the patient must

Proprietary Information of MD Anderson

be monitored closely and prophylactic measures must be taken in high-risk situations. For patients who are deemed very high-risk for venous thromboembolism, the treating physician should strongly consider prophylactic doses of low molecular weight heparin (i.e. enoxaparin 40 mg subcutaneously daily). All patients who develop a deep venous thromboembolism in any location must be treated appropriately with low molecular weight heparin. Heparin should continue for at least 3 months, however treating physician discretion is allowed. Study treatment is to continue during heparin use. For subjects in whom low molecular weight heparin is contraindicated (i.e., renal impairment), a non-vitamin K antagonist anti-coagulant can be used instead where medically appropriate.

Warfarin and Other Vitamin K Antagonists

Warfarin and similar vitamin K antagonists are not permitted during this trial. They should not be given within 30 days prior to initiation of ibrutinib.

6.1.2.3 Antiplatelet and Anticoagulation

VTE prophylaxis is discussed in Section 6.1.2.2. Warfarin or similar vitamin K antagonists should not be administered concomitantly with ibrutinib. Supplements such as fish oil and vitamin E should be avoided. Fatal bleeding events have occurred in patients treated with ibrutinib. Grade 3 or higher bleeding events (subdural hematoma, gastrointestinal bleeding, hematuria and post procedural hemorrhage) have occurred in up to 6% of patients. Bleeding events of any grade, including bruising and petechiae, occurred in approximately half of patients treated with ibrutinib. The mechanism for the bleeding events is not well understood. Ibrutinib may increase the risk of hemorrhage in patients receiving antiplatelet or anticoagulant therapies. Recommend holding ibrutinib for at least 7 days pre and post major surgery and at least 3 days pre and post minor surgery.

6.1.2.4 QT prolongation

Any medications known to cause QT prolongation (Appendix 13.5) should be used with caution; periodic ECG and electrolyte monitoring should be considered. For an up to date list of drugs that cause QT prolongation, please refer to the following website: www.QTdrugs.org

6.1.3 Prohibited Concomitant Therapy

Chemotherapy, anti-cancer immunotherapy, corticosteroids for lymphoma treatment (at doses >10mg of prednisone or equivalent), experimental therapy, or radiotherapy are prohibited during the Treatment phase.

6.1.3.1 Concomitant use of Systemic Corticosteroids

Systemic corticosteroid use at doses above 10mg/day (prednisone or equivalent) is prohibited during the Treatment Phase. Systemic corticosteroid doses above 10mg/day (prednisone equivalent) are allowed for tumor flare reaction treatment (<14 days), \geq grade 3 rash where clinically indicated, or rituximab cytokine release syndrome prophylaxis and treatment of infusion related reactions at any

Proprietary Information of MD Anderson

time. For patients receiving systemic corticosteroids at doses > 10mg/day (prednisone equivalent), a 28 day washout period prior to Cycle 1 Day 1 is required.

6.2 Guidelines for Perioperative management of Ibrutinib

Ibrutinib may increase risk of bleeding with invasive procedures or surgery. The following guidelines should be applied for the use of ibrutinib in the perioperative period for subjects who require surgical intervention or an invasive procedure while receiving ibrutinib:

- For any surgery or invasive procedure requiring sutures or staples for closure, ibrutinib should be held at least 7 days prior to the intervention and should be held at least 7 days after the procedure and restarted at the discretion of the investigator when the surgical site is reasonably healed without serosanguinous drainage.
- For minor procedures (such as central line placement, needle biopsy, thoracentesis, or paracentesis) ibrutinib should be held for at least 3 days prior to the procedure and not be restarted for at least 3 days after the procedure. For bone marrow biopsies that are performed while the subject is on ibrutinib, it is not necessary to hold ibrutinib for these procedures.
- For emergency procedures, ibrutinib should be held at least for 7 days after the procedure and until the surgical site is reasonably healed.

7. STUDY PROCEDURES

Before study entry (Screening Phase), throughout the Treatment Phase, and during Follow-up, various clinical and diagnostic laboratory evaluations are outlined. The purpose of obtaining these measurements is to ensure adequate safety and tolerability. Clinical evaluations and laboratory studies may be repeated more frequently if clinically indicated. The Schedule of Assessments is provided in Appendix 1.

